7.7.1 Missing Data Management

There will be no imputation or replacement of missing data. All analyses will be conducted on observed cases.

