7.3. Variables

The described variables are classified into two variable groups according to the role, the clinical outcome and baseline (demographic, clinical, treatment variables). The latter include the possible subgroups to consider. These analyses are initially exploratory to the extent that the specific analyses may be performed according to the sample collected.

Table 1. Table of Variables

Variable	Role	Data source (s)	Operational definition
Age	Demographic characteristic	Medical record	Birthday
Gender	Demographic characteristic	Medical record	Male, female, other
Race	Demographic characteristic	Medical record	White, half-breed, indigenous, black, others
Weight	Demographic characteristic	Medical record	Kg
Height	Demographic characteristic	Medical record	Mt (meters)
Body mass index	Demographic characteristic	Medical record	Kg/mt ²
City of residence	Demographic characteristic	Medical record	Cities of Colombia
Time to diagnosis to NVAF	Clinical characteristic	Medical record	Date (dd/mm/yy)
High alcohol intake at OAC prescription date	Clinical characteristic	Medical record	Yes, No

Variable	Role	Data source (s)	Operational definition
Diabetes	Clinical characteristic	Medical record	No, without chronic complication, with end-organ damage
Liver disease	Clinical characteristic	Medical record	No, mild, moderate, severe
Hypertension	Clinical characteristic	Medical record	Diagnosis of hypertension (Yes, No)
Uncontrolled hypertension at OAC prescription date	Clinical characteristic	Medical record	Yes, No
Rheumatic disease	Clinical characteristic	Medical record	Yes, No
Acquired Immune Deficiency Syndrome (AIDS)	Clinical characteristic	Medical record	Yes, No
Severe renal disease (dialysis, organ transplant)	Clinical characteristic	Medical record	Yes, No
Moderate renal disease (creatinine > 3 mg/dL)	Clinical characteristic	Medical record	Yes, No
Chronic heart failure	Clinical characteristic	Medical record	Yes, No
Myocardial infarction	Clinical characteristic	Medical record	Yes, No
Chronic obstructive pulmonary disease (COPD)	Clinical characteristic	Medical record	Yes, No
Peripheral vascular disease	Clinical characteristic	Medical record	Yes, No
Stroke or transient ischemic attack (TIA)	Clinical characteristic	Medical record	Yes, No
Dementia	Clinical characteristic	Medical record	Yes, No
Hemiplegia	Clinical characteristic	Medical record	Yes, No
Connective tissue disease	Clinical characteristic	Medical record	Yes, No

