Leukemia	Clinical characteristic	Medical record	Yes, No

PFIZER CONFIDENTIAL

Variable	Role	Data source (s)	Operational definition
Malignant lymphoma	Clinical characteristic	Medical record	Yes, No
Peptic ulcer disease	Clinical characteristic	Medical record	Yes, No
Metastatic solid tumor	Clinical characteristic	Medical record	Yes, No
History of ischemic or hemorrhagic stroke	Clinical characteristic	Medical record	Yes, No
History of TIA	Clinical characteristic	Medical record	Yes, No
History of de tromboembolismo	Clinical characteristic	Medical record	Yes, No
Enfermedad coronaria	Clinical characteristic	Medical record	Yes, No
History of de hemorragia gastrointestinal	Clinical characteristic	Medical record	Yes, No
History of Intracranial bleeding	Clinical characteristic	Medical record	Yes, No
History of Other bleeding	Clinical characteristic	Medical record	Yes, No
Bleeding history or predisposition at start OAC treatment	Clinical characteristic	Medical record	Yes, No
INR > 60% at start OAC treatment	Clinical characteristic	Medical record	Yes, No
Use of aspirin at start OAC treatment	Clinical characteristic	Medical record	Yes, No
Use of clopidogrel at start OAC treatment	Clinical characteristic	Medical record	Yes, No
Use of NSAIDs at start OAC treatment	Clinical characteristic	Medical record	Yes, No
HASBLED at start OAC treatment	Clinical characteristic	Medical record	Score – number higher than 0
CHA2DS2-VASc at start OAC treatment	Clinical characteristic	Medical record	Score – number higher than 0
Anaemia at start OAC treatment	Clinical characteristic	Medical record	Yes, No
Stroke	Clinical outcome	Medical record	Yes, No
Time to stroke	Clinical outcome	Medical record	Date of event dd/mm/yy

Pfizer Confidential

Variable	Role	Data source (s)	Operational definition
Type of stroke	Clinical outcome	Medical record	Ischemic stroke, Haemorrhagic or not specified
Pulmonary embolism	Clinical outcome	Medical record	Yes, No
Time to pulmonary embolism	Clinical outcome	Medical record	Date of event dd/mm/yy
Gastrointestinal bleeding	Clinical outcome	Medical record	Yes, No
Time to gastrointestinal bleeding	Clinical outcome	Medical record	Date of event dd/mm/yy
Intracranial bleeding	Clinical outcome	Medical record	Yes, No
Time to Intracranial bleeding	Clinical outcome	Medical record	Date of event dd/mm/yy
Other major bleeding	Clinical outcome	Medical record	Yes, No
Time to other major bleeding	Clinical outcome	Medical record	Date of event dd/mm/yy
CCI			

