7.3.1. Definition of outcome variables

- **OAC escalation:** The dose escalation of the OAC dose will be considered as a dose frequency according to the index dose, as well as the follow-up doses. The proportion of patients experiencing "dose increase", "dose decrease" or "no change" during follow-up with respect to the index dose will be measured, and the time to dose increase or decrease will be calculated.

C
C
I

C
C
I

- **Switch of treatment:** A switch among anticoagulants will be defined as a prescription filled for non-index anticoagulants within +/- 30 days after the date of discontinuation.
- **Persistence:** Persistence will be defined as the time under OAC therapy, calculated as the time in days from the index date to the date of discontinuation or change to treatment. As previously stated, discontinuation will be defined as a change of treatment, that is, to another OAC, or when there is no evidence of a prescription for 60 days from the last supply delivered, whichever comes first.

Therefore, if a patient does not receive his next prescription for the OAC therapy within 60 days after the end of the previous prescription, it will be considered that he discontinued therapy, and the date of the last prescription will be considered as the final date of persistence.

Persistence with OAC therapy will be considered during the period of individual patient follow-up. Patients will be censored at the end of their follow-up period.

- **Major bleeding:** Patients presenting any of the following diagnoses during the follow-up period:

ICD-10	Description
I60	Subarachnoid haemorrhage
I61	Intracerebral haemorrhage
I62	Other nontraumatic intracranial haemorrhage
I690	Sequelae of subarachnoid haemorrhage
I691	Sequelae of intracerebral haemorrhage
I692	Sequelae of other nontraumatic intracranial haemorrhage
S064	Epidural haemorrhage
S065	Traumatic subdural haemorrhage
S066	Traumatic subarachnoid haemorrhage
I850	Oesophageal varices with bleeding
K250	Acute with haemorrhage

Apixaban

B0661148- NON-INTERVENTIONAL STUDY PROTOCOL

Final, 10 October 2019

ICD-10	Description
K252	Acute with both haemorrhage and perforation
K254	Chronic or unspecified with haemorrhage
K256	Chronic or unspecified with both haemorrhage and perforation
K260	Acute with haemorrhage
K262	Acute with both haemorrhage and perforation
K264	Chronic or unspecified with haemorrhage
K266	Chronic or unspecified with both haemorrhage and perforation
K270	Acute with haemorrhage

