7.7 Data Analysis

This type of analysis is descriptive and explanatory, as it depends largely on the sample size. Continuous variables will be presented as means, standard deviation or other measures of central tendency or position, while categorical variables will be presented as frequencies and percentages.

Regarding bivariate analyses of continuous variables with normal behavior, the Student's t test will be performed. In case of presenting non-normal behavior, the Mann-Withney test will be used. For variables that are continuous with several categories, analysis of variance (ANOVA) will be assessed. In the event of presenting a non-normal behavior, the multivariate analysis of

variance (MANOVA) test will be carried out. For categorical variables, the X² test will be used.

Exploratory analyses based on sample size:

The cumulative incidence of clinical outcomes (Stroke/ systemic embolism and major bleeding) will be calculated throughout the study period, from which the incidence or survival curves will be derived using the Kaplan Meier method. Incidence of events will be explored in clinically relevant subgroups based on sample size.

For the execution of the analysis, CCI and change of treatment, and missing treatments are considered as censures. Treatment comparison will be not conducted.

A similar analysis will be performed for the group of patients who have not presented stroke/ systemic embolism or major bleeding events to estimate the time for CCI change of treatment.

In the independent variables, the significance will be analyzed, as a level of statistical significance p < 0.05.

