7.8 Quality Control

The Principal Investigator or his designee will validate the database constructed, based on the information collected, and they will verify the following:

- Review of illogical data or outliers.
- Verification of conflicting data.
- Review of very high response percentages, such as "unknown" or "not available data"
- Verification of the accuracy of the data collected compared to the source documents
- Report of adverse events (AE)

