7.9 Limitations of the research methods

This study, as other observational studies, has some limitations; these are the result of the type of study and the source of information used. It is possible that there is some misclassification of the diagnoses of patients with NVAF as in turn in the diagnoses of the outcomes. For example, in the medical record, it is possible for the Investigator to use indirect information or to relate some type of approximation to obtain the variable or information of interest or to perform. Although this is a risk, the presence has been mitigated through a clear definition of the outcomes and with the case report format, which allows the Investigator to extract the relevant information only.

As for the claim database, a limitation is that prescription does not indicate whether the patient actually took the therapy as prescribed in both dosage and frequency.

On the other hand, this study will not obtain information related to hospitalizations of patients during the follow-up period; therefore, in the event of having any during this period it will not be known if the patient continued therapy. It is worth noting that these types of limitations are not differential among the cohorts of therapies to assess.

In spite of the limitations previously described, this information is very valuable, especially because it allows linking the claim information of medications with the medical records of each patient, providing a large sample size with a significant number of variables.

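### Read literally, the observed-case rule keeps confirmed strokes, embolisms and bleeds with incomplete dates out of the Kaplan-Meier analysis, and the plan does not say how charts silent on a condition are counted

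*Combined protocol and SAP*

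**What the plan says.** Section 7.7.1 is the complete missing-data rule and lists no exceptions: "There will be no imputation or replacement of missing data. All analyses will be conducted on observed cases".

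On outcomes, Table 1 (section 7.3) holds stroke and each type of bleeding as a Yes/No field from the medical record. The matching time variable is defined as "Date of event dd/mm/yy". Section 7.3.1 identifies major bleeding from an ICD-10 list: "Patients presenting any of the following diagnoses during the follow-up period". Section 7.7 says that "the incidence or survival curves will be derived using the Kaplan Meier method". No section says what happens to an event whose date is only partly known.

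On baseline conditions, Table 1 takes most comorbidities from the medical record as Yes or No, while Table 2 and the risk scores define them largely by ICD-10 lists. Section 7.7 says that "categorical variables will be presented as frequencies and percentages" but gives no denominator. Section 7.8 foresees unknown and unavailable answers, but only as a data-quality check. Section 7.1 treats patients without access to the medical record as missing.

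**The concern.** One short rule covers two situations in which it may not be neutral.

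The first is event dates. Because the event and its date are separate fields, a record can hold a confirmed event with an incomplete date. Kaplan-Meier needs a time for every event. If the date may not be completed and only observed cases are analysed, the event cannot be used. Patients without an event have no event date to lose, so the loss falls on one side only. Incidence of stroke/systemic embolism and major bleeding, the exploratory objective, would be too low.

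The second is silence in the chart. If a chart that does not mention a condition is entered as missing, that patient leaves the percentage for that condition and any score that uses it. If the same silence is read through the code lists, the patient counts as not having the condition. The same chart can therefore give two results for a primary objective, and the plan does not choose between them.

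**Working it through.** The documents give no event rate, comorbidity prevalence or missing fraction. The 7,500 patients in section 7.5 are a database count with no calculation behind it, so there is no planned figure to reproduce. Every rate below is an assumption.

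**Event dates.** Let r be the true proportion with an event and m the share of events without a full date.

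- Patient dropped: r(1 − m)/(1 − rm)
- Patient kept, event not counted: r(1 − m)

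With r = 5%, 7,500 patients give 375 events. For m = 10%, 37.5 patients are lost on average, and 0.05 × 0.90/(1 − 0.005) = 0.0450/0.995 = 4.52%.

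| m | Dropped | Kept as non-event | Relative change if dropped |
|---|---|---|---|
| 2% | 4.91% | 4.90% | −1.9% |
| 5% | 4.76% | 4.75% | −4.8% |
| 10% | 4.52% | 4.50% | −9.5% |
| 20% | 4.04% | 4.00% | −19.2% |

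Both readings lower the estimate, by about the share of undated events. Keeping these events returns 5.00%.

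A Kaplan-Meier simulation checked the direction under censoring. It assumed an event hazard of 3% per year, a censoring hazard of 40% per year, and administrative censoring between 1 and 6.5 years. One-year incidence was 2.95% with all events, and 2.82%, 2.68% and 2.39% after dropping 5%, 10% and 20% of patients with events.

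**Silent charts.** Let p be the true prevalence, a the probability that a present condition is stated, and b the probability that an absent one is explicitly denied.

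- Charts stating Yes or No only: pa/(pa + (1 − p)b)
- Silence counted as No: pa

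With p = 30%, a = 1 and b = 0.7: 0.30/(0.30 + 0.70 × 0.7) = 0.30/0.79 = 38.0%.

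| a | b | Yes/No charts only | Silence as No |
|---|---|---|---|
| 1.00 | 0.90 | 32.3% | 30.0% |
| 1.00 | 0.70 | 38.0% | 30.0% |
| 1.00 | 0.50 | 46.2% | 30.0% |
| 0.95 | 0.70 | 36.8% | 28.5% |
| 0.80 | 0.80 | 30.0% | 24.0% |
| 0.70 | 0.90 | 25.0% | 21.0% |

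The observed-case percentage is too high only when absent conditions go unstated more often than present ones (b < a). It is unbiased when a = b and too low when b > a.

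**The case against.** The strongest reply is that the plan nowhere says that undated events are dropped or that percentages use only charts stating Yes or No. Both are inferences from a brief text. That is correct, and the point rests on a literal reading of 7.7.1.

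Outcomes are diagnoses found in the medical record, so a dated entry may usually exist. Section 7.9 accepts that the abstractor may approximate. Section 7.6.1 plans completion instructions and data-entry guidelines that could hold a partial-date convention. This stands as a reason to expect few undated events. It does not settle the matter: no such convention is written, and approximating a date sits badly with 7.7.1. The major-bleeding list also contains sequelae codes (I690 to I692), for which the encounter date need not be the date of the bleed.

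Three stronger readings are tempting but unsupported.

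- *Incomplete dates are common because hospital data are absent.* Section 7.9 does say that "this study will not obtain information related to hospitalizations of patients during the follow-up period", but the consequence it draws concerns only whether therapy continued. The documents do not show how often dates are incomplete.
- *Prevalence is overstated.* The Yes/No fields and code lists allow silence to be read as No, in which case nothing is missing. Even when silence is treated as missing, the direction can reverse.
- *Few patients would have a complete risk score.* CHA2DS2-VASc has only five diagnosis-based components; the rest are age and sex. With 5% or 10% of charts silent per item, completeness would be 0.95^5 = 77% or 0.90^5 = 59%. Even this assumes that items are silent independently. If the same poorly documented charts are silent on many items, completeness is higher.

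It is also fair that incidence is exploratory and that no treatment comparison is planned. This limits the weight of the point but does not remove the gap.

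**Conclusion.** The event-date part holds on a literal reading of 7.7.1: a confirmed event with an incomplete date cannot enter as an event, and this can only lower incidence. The relative loss is slightly below the share of undated events, so a true 5.0% would be reported as 4.9% to 4.0% if that share is 2% to 20%. The share is an assumption and may be at the low end.

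The silent-chart part is a conditional clarification. If silence is coded as missing, comorbidity percentages and scores rest on the better-documented charts. Prevalence may then be overstated, provided that absent conditions are left unstated more often than present ones. That is plausible in chart review but not established by the documents.

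The amendment is worth making because it is cheap, but the documents do not show that the results would be materially wrong without it.

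**What to change.** Amend section 7.7.1 with three rules.

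1. A confirmed outcome is never dropped for an incomplete date. Assign a prespecified date within the known interval, for example the midpoint between the last note without the event and the first note that mentions it. Repeat the analysis with the earliest and the latest possible dates. The midpoint is one convention among several; what matters is to fix it in advance and show the bounds.
2. For diagnosis-based items and score components, among patients whose medical record was accessed, no record of the condition counts as absent. Patients without record access stay missing, as in section 7.1.
3. Observed-case analysis is kept for measured or asked items such as weight, height, race, alcohol intake and INR, with n/N and percent missing reported for each. The INR component of HAS-BLED is measured rather than coded, so state how that score is formed when no INR exists.

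The cost is a few sentences of protocol text and two sensitivity runs. The rules are best set before abstraction, so that the template captures partial dates and separates not mentioned from denied. Completed dates carry some timing error. Rule 2 understates prevalence slightly if nearly all present conditions are recorded (28.5% for a true 30% at 95% recording), but by more if recording is poor (24.0% at 80%). The number of silent charts per item should therefore be reported beside the percentage.

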7.8 Quality Control

The Principal Investigator or his designee will validate the database constructed, based on the information collected, and they will verify the following:

- Review of illogical data or outliers.
- Verification of conflicting data.
- Review of very high response percentages, such as "unknown" or "not available data"
- Verification of the accuracy of the data collected compared to the source documents
- Report of adverse events (AE)

7.9 Limitations of the research methods

This study, as other observational studies, has some limitations; these are the result of the type of study and the source of information used. It is possible that there is some misclassification of the diagnoses of patients with NVAF as in turn in the diagnoses of the outcomes. For example, in the medical record, it is possible for the Investigator to use indirect information or to relate some type of approximation to obtain the variable or information of interest or to perform. Although this is a risk, the presence has been mitigated through a clear definition of the outcomes and with the case report format, which allows the Investigator to extract the relevant information only.

As for the claim database, a limitation is that prescription does not indicate whether the patient actually took the therapy as prescribed in both dosage and frequency.

On the other hand, this study will not obtain information related to hospitalizations of patients during the follow-up period; therefore, in the event of having any during this period it will not be known if the patient continued therapy. It is worth noting that these types of limitations are not differential among the cohorts of therapies to assess.

In spite of the limitations previously described, this information is very valuable, especially because it allows linking the claim information of medications with the medical records of each patient, providing a large sample size with a significant number of variables.

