 - Pregnancy during the study period. ICD-10 O00-O9A
 - Diagnosis of venous thromboembolism (VTE) – ICD-10 codes: I26, I80 - I82;
- Individuals with a transitory diagnosis of NVAF prior to the use of the treatments of interest or index date;
- Exposure to more than one OAC on or after the index date, during the follow-up period;
- NOAC doses different from those recommended by the manufacturing laboratories.

Data Collection:

PFIZER CONFIDENTIAL

The information will be analyzed in two moments: (i) the period of the index date, where the baseline information of patients will be collected; (ii) and the follow-up period, during this period the clinical results will be evaluated as well as the continuation of the treatment in the study population and for specific subpopulations.

Variables:

- Clinical and demographic characteristics
- Treatment patterns (OAC usage, dose, concomitant medications, persistence)

Effectiveness outcomes:

- First CCI switch of treatment, first event of stroke/ systemic embolism

Safety outcomes:

- Major bleeding

C
C

Data sources:

The information will be used in the study comes exclusively from secondary sources.

- Claim database:
 - The persistence on therapy and treatment patterns (duration of treatment, changes, persistence), pharmacy claim information, demographic information, diagnosis and insurance data.
- Medical records:
 - Baseline demographic and clinical characteristics and the information related to the outcomes of interest (stroke/systemic embolism, bleeding events and death)

Statistic analysis

This type of analysis is descriptive and explanatory, as it depends largely on the sample size. Continuous variables will be presented as means, standard deviation or other measures of central tendency or position, while categorical variables will be presented as frequencies and percentages.

Regarding bivariate analyses of continuous variables with normal behavior, the Student's t test will be performed. In case of presenting non-normal behavior, the Mann-Withney test will be used. For variables that are continuous with several categories, analysis of variance (ANOVA) will be assessed. In the event of presenting a non-normal behavior, the multivariate analysis of variance (MANOVA) test will be carried out. For categorical variables, the χ^2 test will be used.

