7.4.2. Medical Record

Of the patients identified from the claim database, information will be extracted from the second database, the medical record, it will serve to characterize patients based on their baseline demographic and clinical characteristics, that is, on the index date. In turn, it contains the main control variables and the information related to the outcomes of interest, stroke and bleeding events.

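### Hospitalization data are not obtained, yet stroke, systemic embolism and major bleeding come only from a medical record whose inpatient content is not stated; events may be under-captured, and the curves should be labelled as recorded events

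*Combined protocol and SAP*

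**What the plan says.** Section 7.9 states that "this study will not obtain information related to hospitalizations of patients during the follow-up period". The consequence it gives is that "in the event of having any during this period it will not be known if the patient continued therapy". It then asserts that "these types of limitations are not differential among the cohorts of therapies to assess". Earlier, the same section concedes in general terms that "It is possible that there is some misclassification of the diagnoses of patients with NVAF as in turn in the diagnoses of the outcomes", and says that clear outcome definitions and the case report format mitigate this.

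The outcomes have a single source. Section 7.4.2 says the medical record holds "the information related to the outcomes of interest, stroke and bleeding events". The abstract says it supplies "the information related to the outcomes of interest (stroke/systemic embolism, bleeding events and death". Table 1 in section 7.3 records each visible event as Yes or No from the medical record, with a separate field for the date of the event.

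Section 7.7 plans that "The cumulative incidence of clinical outcomes (Stroke/ systemic embolism and major bleeding) will be calculated throughout the study period", with Kaplan-Meier curves. Section 7.7.1 allows no imputation. Section 7.1 ends follow-up at discontinuation, switch, death, a first outcome event or the end of the study. Section 7.3.1 declares discontinuation when 60 days pass without a new supply, and dates the end of persistence back to the last prescription.

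**The concern.** Cerebral infarction, arterial embolism and intracranial haemorrhage are all on the outcome code lists, and they are acute events commonly treated in hospital. If the accessible record is mainly ambulatory, such an event enters it only when someone notes it later, and a fatal one may never be noted. The mitigation in section 7.9 does not help here: a clear definition and a good form cannot recover an event that never reached the record. The visible outcome fields offer no category for patients in whom an event could not have been seen, so a missed event can become a No.

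At stake is what the study can conclude. Readers would naturally take the curves as the incidence of stroke and bleeding in Colombian NVAF patients on anticoagulants. The plan supports a narrower statement about recorded events, and neither section 7.7 nor section 7.9 says so.

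**Working it through.** **Nothing to reproduce.** The protocol gives no event rate, precision target or capture rate. The 7,500 in section 7.5 is a count of eligible patients. All rates below are assumptions, used to show direction and scale.

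**Step 1: how a hospital event passes through the rules.**
- *Survivor, noted later.* The event is captured. Table 1 asks for the event date, so it can be dated correctly.
- *Survivor, never noted, still collecting drug.* The event field can read No, and follow-up can continue as event-free.
- *Admitted for long, or dead, and no longer collecting drug.* Let the last prescription be on day L, its supply end on day L + s, and the unrecorded event fall on day E, after L. With no new supply by day L + s + 60, the patient is classed as discontinued and persistence ends on day L. If outcome follow-up ends on that same date, the patient is censored at L, before E. The censoring is then related to the outcome. Part of the discontinuation text is blacked out, so this follows the visible wording.

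**Step 2: the downward pull.** Let p be the true one-year risk, Se the captured share of true events, and f the share of event-free patients falsely coded.

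Observed risk = Se × p + f × (1 − p)

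Take p = 2%, so 0.02 × 7,500 = 150 true events:

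| Se | Events captured | Observed, f = 0 | Observed, f = 1% | Break-even f |
|---|---|---|---|---|
| 0.5 | 75 | 1.0% | 1.98% | 1.02% |
| 0.7 | 105 | 1.4% | 2.38% | 0.61% |
| 0.9 | 135 | 1.8% | 2.78% | 0.20% |

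With f = 0, the observed risk falls in proportion to capture. Over p from 1% to 4% it runs from 0.5 × 1% = 0.5% to 0.9 × 4% = 3.6%.

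**Step 3: is the net effect downward?** The break-even false-positive share is (1 − Se) × p / (1 − p). For Se = 0.7 and p = 2% it is 0.3 × 0.02 / 0.98 = 0.61%. Above that, the observed risk exceeds the true one. The major bleeding list in section 7.3.1 makes false positives plausible. It includes sequelae of intracranial haemorrhage (I690 to I692), which can reflect a past event, and codes with no severity criterion such as R04, R31 and H922. The stroke and embolism lists do not have these features to the same degree.

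**Step 4: death in Kaplan-Meier.** The list of censoring reasons in section 7.7 is partly blacked out, so the handling of death cannot be confirmed. If death is censored, 1 − KM = 1 − exp(−ht), whereas incidence with death as a competing event is h/(h + d) × (1 − exp(−(h + d)t)). Assume an event hazard h of 2% a year and t = 5 years. Then 1 − KM is 9.52%. At death hazards d of 3%, 5% and 10% a year, the competing-risk incidence is 8.85%, 8.44% and 7.52%. The ratios are 1.076, 1.128 and 1.265, an overstatement of about 8% to 27%. This upward pull would apply to stroke and embolism as well as bleeding.

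**Step 5: does adding deaths give an upper bound?** No. Survivors' unrecorded events stay missed. If 15% to 30% of events were fatal before any later chart entry, and 60% to 90% of survivors' events were recorded, the share still missing would be between 0.85 × 0.10 = 8.5% and 0.70 × 0.40 = 28% of true events.

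**The case against.** The strongest case on the other side has five parts.

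- **The record may hold hospital events.** The protocol nowhere excludes inpatient or discharge documents. The abstract expects stroke, bleeding and death from the record, and section 7.3.1 takes ischemic stroke from diagnoses in the medical history, where a hospital event can be noted. The hospitalization sentence can be read as concerning drug exposure during admission. This stands: the supported wording is that events may be missed, not that they are.
- **Dating is already specified.** A reader might infer that events are dated at the later visit and so shifted late. Table 1 asks for the date of the event, so that inference fails. What is missing is a flag for events first documented retrospectively.
- **The incidence is not shown to be a lower bound.** A reader might infer that it is, since hospital capture appears absent. Steps 3 and 4 show why this does not follow: the bleeding codes and a possible censoring of deaths can both push the estimate up.
- **Unseen patients are partly covered.** Section 7.2 restricts the cohort to accessible records, and section 7.1 treats patients lost to follow-up, changing HMO or without record access as missing. This narrows the problem. It leaves patients who still collect drug but have no later chart contact.
- **The outcomes are exploratory and descriptive.** Section 7.7 rules out treatment comparison, and section 7.9 admits outcome misclassification. This limits the consequences. It does not remove the need to say what the curves measure, because the general caveat is not tied to hospital care and its stated mitigation cannot recover unrecorded events.

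**Conclusion.** The concern holds in a limited form. The protocol declares a gap in hospitalization data, applies it only to persistence, and plans Kaplan-Meier incidence for acute outcomes from a record whose inpatient content it does not describe. Severe events may be under-captured, and the discontinuation rule can turn an unrecorded event into an earlier censoring.

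Under-capture itself acts downward and matters most plausibly for ischemic stroke and systemic embolism. For major bleeding the net direction is unknown. The size is unknown for every outcome, and the percentages in the working are illustrations under assumed risk, capture and death rates.

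The statement that limitations do not differ between cohorts has no support in the protocol. Table 1 collects monthly INR from the medical record for warfarin patients only. If that reflects more frequent chart contact, warfarin events have more chances of being recorded. No formal comparison is planned, but section 7.2.3 defines cohorts by drug and section 7.7 explores incidence in subgroups, so unequal capture could still mislead.

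This should be changed before abstraction and analysis. It affects what may be concluded from the exploratory curves, not the primary description of patients and treatment patterns.

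**What to change.** 1. In sections 6, 7.7 and 7.9, name the outcomes *first stroke/systemic embolism, or major bleeding, recorded in the accessible medical record*. Do not present the curves as complete incidence, and do not call them a lower bound.
2. Add two sensitivity analyses for each outcome: a curve for recorded event or death, not described as an upper bound, and a curve in which event-free time ends at the last chart contact.
3. Keep the event-date field in Table 1 and add a flag for events first documented retrospectively.
4. In section 7.9, extend the hospitalization limitation to outcome under-ascertainment, state whether inpatient and discharge documents and deaths are in the record, and support or remove the statement that limitations do not differ between cohorts.

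The cost is protocol wording, one abstraction flag and a few extra curves. The last-chart-contact analysis also needs the date of last chart contact, and it has somewhat shorter outcome follow-up. The study gives up a broad incidence claim for a more limited one.
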